### 2.2 Secondary objectives

1. To determine whether presurgical treatment with Letrozole suppresses IRS-1/PI3K/AKT pathway activation compared to baseline.
2. To determine whether the level of IRS-1/PI3K/AKT pathway activation is correlated with rate of tumor cell proliferation as determined by Ki67 score.
3. To determine whether RAD001-induced changes in IRS-1/PI3K/AKT signaling *ex vivo* are correlated with rate of tumor cell proliferation as determined by Ki67 score.
4. To identify changes in mRNA levels of ER-regulated gene induced by presurgical treatment with Letrozole.

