**5.5.2. Immunohistochemical analysis of pre- vs. post-Letrozole tumors.**  
Baseline (diagnostic core biopsy specimen) and post-Letrozole (surgical specimen) tumor samples will be sectioned and processed for IHC in the Pathology Translational Research Shared Resource. Tissue sections will be immunostained using antibodies against ER, PR, and Ki67. ER and PR

will be scored using a Histoscore scale (23); we expect Letrozole treatment to decrease PR levels, while ER may be unaffected. Ki67 will be scored by counting the number of positively-stained cells in 10 high-power (400x magnification) microscopic fields (24, 25). Pre- and post-Letrozole Ki67+ cell counts will be compared by t-test; Letrozole treatment should induce an overall decrease in Ki67 score.

The primary goal of this analysis is to determine whether changes in signaling induced by RAD001 treatment *ex vivo* are associated with Ki67 score. A higher post-anti-estrogen Ki67 score, and a smaller decrease in Ki67 score in response to presurgical treatment with an anti-estrogen, are associated with shorter recurrence-free survival (26). Hence, it is thought that a higher level of residual tumor cell proliferation (higher Ki67 score) following anti-estrogen treatment, or a weaker biological response (change in Ki67 score) to anti-estrogen treatment, are indicative of less dependence of tumor cells on ER for growth and survival. Our preclinical data indicate that ER drives IRS-1 and IGF-1R expression, which facilitate RAD001-induced PI3K/AKT activation. Therefore, in tumors that are less dependent upon ER, Letrozole treatment is expected to have less of an effect on IRS-1/PI3K/AKT signaling. Such findings would support the use of combinations of anti-estrogens and mTORC1 inhibitors in patients with ER-driven tumors.

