## 9.0 STATISTICAL CONSIDERATIONS

9.1 PRIMARY ENDPOINT – The primary endpoint of this trial is the level of IRS-1/PI3K/AKT pathway activation in primary tumors, measured by densitometric analysis of immunoblot signals of markers of pathway activation (IRS-1, phospho-IRS-1-Ser636/639, phospho-AKT-T308, phospho-AKT-S473).

9.2 SECONDARY ENDPOINT – The secondary endpoint is Ki67 score, as determined by the percentage of Ki67+ tumor cells by IHC.

9.3 PRIMARY ANALYSIS PLAN - The primary analyses determine whether RAD001 treatment of tumor samples *ex vivo*, and/or presurgical treatment of patients with Letrozole, alter IRS-1/PI3K/AKT pathway activation in breast tumors. Signal values of IRS-1, phospho-IRS-1-Ser636/639, phospho-AKT-T308, phospho-AKT-S473 will be determined by densitometric analysis of immunoblots. Below is an illustration of projected data and relevant comparisons. Signal values of control (DMSO)-treated and RAD001-treated tumor samples will be compared using a 2-sided paired t-test. These tests will be performed separately in tumors from each arm of the study (*i.e.*, untreated, or letrozole-treated, as shown below in *left* and *center* panels). An additional test will compare the magnitude of change in signal values in Arm A vs. Arm B (2-sided independent t-test), to determine whether Letrozole treatment alters response to RAD001 (shown below in *right* panel).

9.4 SECONDARY ANALYSIS PLAN – Secondary analysis to determine whether presurgical treatment with Letrozole suppresses IRS-1/PI3K/AKT activation compared to baseline will be achieved using a paired t-test comparing IRS-1/PI3K/AKT pathway markers scored by IHC analysis of matching tumor samples from patients acquired A) at baseline (diagnostic biopsy) and B) at surgery (post-Letrozole). We will also determine whether tumor Ki67 IHC score is associated with the level of IRS-1/PI3K/AKT pathway activation, or with RAD001-induced changes in IRS-1/PI3K/AKT signaling, by Spearman correlation between Ki67 score and densitometric signal values of pathway markers as determined by immunoblot analysis or IHC Histoscore.

9.5 STATISTICAL TESTING - All statistical tests will be 2-sided, and the overall type I error will be 0.05.

9.6 SAMPLE SIZE – The primary analyses determine whether RAD001 treatment of tumor samples *ex vivo*, and/or presurgical treatment of patients with Letrozole,

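### The Ki67 correlation in 9.4 serves Objectives 2 and 3 but cannot carry the ER-dependence inference in 5.5.2, because it never relates RAD001 response to the change in Ki67

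*Combined protocol and SAP*

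**What the plan says.** Secondary Objective 3 (section 2.2) asks whether RAD001-induced signaling changes "are correlated with rate of tumor cell proliferation as determined by Ki67 score". Objective 2 asks the same of the pathway level.

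Section 9.2 defines the endpoint: "The secondary endpoint is Ki67 score, as determined by the percentage of Ki67+ tumor cells by IHC". It names neither a specimen nor a change from baseline.

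Section 9.4 gives the test. Ki67 is related to pathway level, or to the changes that RAD001 induces in it, "by Spearman correlation between Ki67 score and densitometric signal values of pathway markers as determined by immunoblot analysis or IHC Histoscore". It does not say which specimen's Ki67 is meant, does not name an arm and does not adjust for baseline.

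Section 5.5.2 opens its interpretation with "The primary goal of this analysis is to determine whether changes in signaling induced by RAD001 treatment" and completes the goal as an association with Ki67 score. It then names two signs of low ER dependence: higher Ki67 remaining after treatment, "or a weaker biological response (change in Ki67 score) to anti-estrogen treatment, are indicative of less dependence of tumor cells on ER". It expects Letrozole to affect signaling less in such tumors, and ends: "Such findings would support the use of combinations of anti-estrogens and mTORC1 inhibitors in patients with ER-driven tumors".

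The same section scores Ki67 on both the diagnostic biopsy and the surgical specimen of Letrozole-treated patients. The one use it names for the baseline value is a group comparison: "Pre- and post-Letrozole Ki67+ cell counts will be compared by t-test". That comparison does not involve RAD001 response.

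**The concern.** The inference and the test do not meet. Of the two ER-dependence markers in 5.5.2, the change in Ki67 has no planned test against RAD001 response. The other, residual Ki67, can be tested under 9.4 only if the unspecified score is taken to be the surgical one, and then as a raw value. A tumor that was proliferating fast at diagnosis can still score high at surgery after an ordinary response to Letrozole.

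Objective 3 itself allows that RAD001 response may track proliferation in general. If it does, the 9.4 correlation will tend to be positive in Arm B with no link to ER dependence. The same result would then fit two explanations, only one of which supports the closing sentence of 5.5.2. In the other direction, spread in baseline Ki67 dilutes a real link with the Letrozole-induced change. Arm A shows the problem most plainly: those tumors receive no Letrozole, so their Ki67 says nothing about response to it, yet 9.4 does not limit the correlation to Arm B.

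**Working it through.** The plan states no effect size, SD or power for this correlation, so there is no figure to reproduce.

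**Inputs from the documents.** Two-sided alpha 0.05 (9.5); Arm B n = 10, 14 or 30 (table in 9.6); Spearman correlation (9.4).

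**Assumptions.** Let b be log baseline Ki67 (SD 1), c the log change from biopsy to surgery (SD k, independent of b), and surgical Ki67 S = b + c. RAD001 response R has unit variance, correlation ρ with b and γ with c. The main case is k = 1.

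**Step 1: size of the mixed correlation.** If R relates only to baseline (γ = 0), then corr(R, S) = ρ/√(1 + k²).
- ρ = 0.5, k = 1: 0.5/1.414 = 0.354
- ρ = 0.3, k = 1: 0.3/1.414 = 0.212

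The correlation of R with c is zero in both cases.

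**Step 2: hand check of the rejection rate.** On the Spearman scale, 0.354 becomes (6/π)·asin(0.354/2) = 0.340, with Fisher z = 0.354. The SE is √(1.06/(n−3)).
- n = 10: SE 0.389; 0.354/0.389 − 1.96 = −1.05; about 15%
- n = 14: SE 0.310; 0.354/0.310 − 1.96 = −0.82; about 21%
- n = 30: SE 0.198; 0.354/0.198 − 1.96 = −0.17; about 43%

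**Step 3: simulation** (8,000 to 10,000 trials per setting, k = 1). Percentage with p < 0.05 at n = 10 / 14 / 30:

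| True state | Surgical Ki67 alone | Change in Ki67 | Surgical Ki67 adjusted for baseline |
|---|---|---|---|
| ρ = 0.5, γ = 0 | 16 / 21 / 45 | 5 / 5 / 5 | 5-6 throughout |
| ρ = 0.3, γ = 0 | 9 / 10 / 18 | 5 / 5 / 5 | 5-6 throughout |
| ρ = 0, γ = 0.6 | 21 / 30 / 61 | 42 / 59 / 92 | 30 / 49 / 89 |

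Repeat runs agree to within about a percentage point. The adjusted test is a partial Spearman correlation with n − 3 degrees of freedom.

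**Step 4: sensitivity to the assumptions.**
- ρ = 0.5 with k = 0.5: surgical Ki67 alone rejects in 23 / 33 / 66%.
- ρ = 0.5 with k = 2: 9 / 11 / 20%.
- ρ = 0.1 with k = 1: about 6% at every n.
- Ki67 measurement error, with b and c independent and ρ = 0.5: at n = 30 the adjusted test rises to about 7-8% for an error SD of 0.4 of the baseline SD, and about 12% for 0.8.
- Correlation of −0.3 between baseline and change: the change-score test rises to about 10% at n = 30.

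**Step 5: where the added tests lose.** With ρ = 0.3 and γ = 0.6 at n = 10, surgical Ki67 alone rejects in about 47%, the change score in 41% and the adjusted test in 38%. Part of the 47% is baseline proliferation rather than ER dependence.

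**The case against.** The strongest reply is that 9.4 tests what the objectives ask. Objectives 2 and 3 concern proliferation rate, 5.5.2 states its goal as association with Ki67 score, and ER dependence is neither an objective nor an endpoint; it appears in rationale text with a conditional ending. This stands. A reader might infer from the rates above that the planned test has an inflated type I error. The documents do not support that: against 9.4's own null, the rates are power to detect a correlation that really exists.

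A reader might also infer that the plan ignores baseline Ki67 altogether. It does not: 5.5.2 uses it in the pre/post t-test. The gap is that 9.4 does not bring it into the RAD001 correlation.

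It can be said that 5.5.2 accepts residual Ki67 as a marker, citing prognostic evidence. That premise need not be disputed. A marker of recurrence can still carry baseline proliferation, and 5.5.2 lists the change as a separate marker.

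It can also be said that no patient has RAD001 response measured before and after Letrozole, since RAD001 is applied only to surgical cores, so no correlation here directly tests whether Letrozole altered that response in a given tumor. This is true, and it limits the added analysis too. The paired IHC comparison in 9.4 does address Letrozole's effect on signaling, but only on average, not whether it varies with ER dependence.

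Finally, the word score might have been meant to include change. The text does not say so, and 9.2 defines it as a percentage. One sentence would settle it.

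**Conclusion.** The concern holds in a limited form. The planned Spearman correlation is sound for Objectives 2 and 3. It does not support the ER-dependence inference in 5.5.2, because the time point and arm are open, the change in Ki67 is never related to RAD001 response, and a surgical score alone cannot separate fast growth at baseline from weak response to Letrozole.

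The size is illustrative. With independent log baseline and log change of equal SD, and a response-baseline correlation of 0.3 to 0.5, a result open to misreading arises in about 9-16%, 10-22% and 18-45% of trials at n = 10, 14 and 30. It is larger if the change varies less than baseline, and close to nominal if the response-baseline correlation is near 0.1. The direction holds whenever response is positively related to baseline proliferation and baseline carries over into the surgical score.

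Severity is minor. The analysis is secondary, the study is a pilot, the inference is conditional, and no enrollment rule, stopping rule or primary conclusion depends on it.

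**What to change.** Keep the simple Spearman correlation for Objectives 2 and 3, stating that it uses Ki67 at surgery and is reported by arm. Add to 9.4:

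> In Arm B, RAD001-induced change in pathway markers will be correlated (Spearman) with the within-patient change in Ki67 from diagnostic biopsy to surgery, on the log scale with a small prespecified offset for zero scores. The partial Spearman correlation with surgical Ki67, adjusted for baseline Ki67, will be reported as a sensitivity analysis. Both are exploratory.

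State in 5.5.2 that any ER-dependence interpretation rests on these Arm B results, and otherwise limit the conclusion to proliferation. The change score leads because it is the plan's own marker and had more power than the adjusted test when response tracks only the change.

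The cost for Arm B is wording: both specimens are already scored for Ki67. Reporting by arm also needs Ki67 on Arm A surgical tissue; 5.5.2 describes staining only for Letrozole-treated patients, so 9.4 should confirm it.

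The downsides are one or two extra exploratory tests per marker and slightly lower power at n = 10 when baseline and change act in the same direction. Neither test removes confounding fully: noisy baseline Ki67 affects the partial correlation, and a correlation between baseline and change affects the change score. That is a reason to report both. Power stays low in a small Arm B (about 42% at n = 10 for the change score, even at a correlation of 0.6), so a null result should not be read as absence of a link.

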alter IRS-1/PI3K/AKT pathway activation in breast tumors. RAD001-induced pathway activation will be defined as a  $\geq 50\%$  increase in phospho-AKT densitometric signal value compared to DMSO-treated control; this scoring system provides a binary metric for sample size determination for Arm B (below). Given that this is a pilot study, we do not know what fraction of ER+/HER2-breast tumors will exhibit RAD001-induced IRS-1/PI3K/AKT activation. Hence, tumors from 10 untreated patients in Arm A will be used to determine the frequency with which RAD001 induces AKT activation.

The fraction of tumors in Arm A (untreated patients) that exhibit RAD001-induced AKT activation will be used to determine the number of patients that need to be enrolled in Arm B (presurgical Letrozole treatment) to detect a significant effect of presurgical Letrozole treatment on RAD001-induced AKT activation. We estimate that  $\leq 15\%$  of Letrozole-treated tumors will exhibit RAD001-induced AKT activation. If we observe that RAD001 increases phospho-AKT in X of 10 tumors in Arm A, we will enroll Y patients in Arm B (presurgical Letrozole) to provide a sufficient number of tumors to detect a significant effect ( $p \leq 0.05$ ) of presurgical Letrozole on RAD001-induced changes in phospho-AKT levels with 80% power (calculated using uncorrected chi-squared statistic). If we observe that  $\leq 3$  tumors from untreated patients in Arm A exhibit RAD001-induced AKT activation, the study will be terminated at this point, and Arm B will not enroll patients. To account for interpatient/intertumor variability, we will enroll a minimum of 10 patients in Arm B.

X (n of tumors from untreated patients that exhibit a <math>\geq 50\%</math> increase in P-AKT levels in response to RAD001 treatment ex vivo)	Y (n of patients to be enrolled in Arm B, presurgical Letrozole)
0-3	Terminate study
4-6	30
7-8	14
9-10	10

- 10.

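### Section 9.5 promises an overall type I error of 0.05, but four primary markers and three comparisons have no multiplicity rule to deliver it

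*Combined protocol and SAP*

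**What the plan says.** Section 9.5: "All statistical tests will be 2-sided, and the overall type I error will be 0.05". The word overall claims control across tests, not for each one.

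Section 9.1 names one primary endpoint, pathway activation, but measures it by four separate immunoblot signals: "markers of pathway activation (IRS-1, phospho-IRS-1-Ser636/639, phospho-AKT-T308, phospho-AKT-S473". They are not combined or ranked.

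Section 9.3 compares RAD001-treated with DMSO-treated tissue by paired t-test, and "These tests will be performed separately in tumors from each arm of the study". It then adds a third comparison: "An additional test will compare the magnitude of change in signal values in Arm A vs. Arm B (2-sided independent t-test". The two treatment questions are joined by and/or, so nothing requires all tests to succeed together.

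Section 9.6 comes closest to choosing a lead marker. It defines RAD001-induced activation as a rise of at least 50%, that is, an "increase in phospho-AKT densitometric signal value compared to DMSO-treated control". It sizes Arm B for an effect at p ≤ 0.05 "on RAD001-induced changes in phospho-AKT levels with 80% power (calculated using uncorrected chi-squared statistic". It does not say whether T308, S473 or both are meant, and section 9.3 does not carry this measure into its t-tests. If 3 or fewer of the 10 Arm A tumours respond (X ≤ 3), Arm B does not open.

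**The concern.** An overall error of 0.05 is a property of the whole set of primary tests. It has to come from somewhere: an adjustment, a testing order, a composite, or a single designated test. I found none of these in the document. As written, a significant result on any one of four markers, in any of three comparisons, could be reported as a primary finding under a 5% overall error rate that the design does not have.

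The gap also reaches the conduct of the trial. Section 5.5.1 treats the two phospho-AKT sites as readouts of different activities (S473 for mTORC2; T308 for PIP3 and PI3K/PDK1). With no site named, it is unclear which signal determines X, and so whether Arm B opens and at what size.

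**Working it through.** **Inputs from the plan.** Four markers (9.1); three comparisons (9.3); Arm A n = 10; Arm B size Y = 30, 14 or 10 for X = 4–6, 7–8 or 9–10, with termination at X ≤ 3 (9.6); Arm B activation rate 15%, p ≤ 0.05, uncorrected chi-squared (9.6).

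**Inputs assumed, because the plan gives none.** Each test at 0.05; t-tests on log ratios (RAD001/DMSO); equal correlation between markers of 0, 0.5, 0.8 or 0.9; SD of the log ratio 0.3, 0.5, 0.8 or 1.2; X counted three ways (one site, either site, both sites up by at least 50%).

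**Step 1: the plan's own sizing.** Power = Φ[(p₁ − p₂ − z·SE₀)/SE₁], with SE₀ the pooled and SE₁ the unpooled standard error, p₁ = X/10, p₂ = 0.15.

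- X = 7, Y = 14: pooled rate (7 + 2.1)/24 = 0.379, SE₀ = 0.2009, SE₁ = 0.1735. At 0.05: (0.55 − 1.960 × 0.2009)/0.1735 = 0.901, power 81.6%.
- X = 6, Y = 30: pooled rate (6 + 4.5)/40 = 0.2625, SE₀ = 0.1607, SE₁ = 0.1681. At 0.05: (0.45 − 1.960 × 0.1607)/0.1681 = 0.804, power 78.9%.

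These rows reproduce the stated 80% only when the full 0.05 goes to one phospho-AKT comparison. (X = 4 and X = 5 with Y = 30 give 40% and 60%, a separate matter.)

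**Step 2: number of tests.** 4 markers × 3 comparisons = 12.

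**Step 3: simple reference values.** For independent tests, the chance of at least one false positive is 1 − 0.95^k: 18.5% for k = 4 and 46% for k = 12. The second figure is too high for this design, because the comparisons share data and Arm B may not open. So the design was simulated.

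**Step 4: simulation.** 40,000 trials per scenario; one-sample t-test on the log ratios in each arm; pooled two-sample t-test between arms; Arm B opened only if X ≥ 4, with Y from the plan's table. Ranges run over the SDs and the three ways of counting X.

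| Chance of at least one false positive, global null | corr. 0 | 0.5 | 0.8 | 0.9 |
|---|---|---|---|---|
| Four Arm A tests | 18.0–19.0% | 15.7–16.4% | 11.8–12.3% | 9.6–10.1% |
| All 12, stopping rule applied | 18.6–37.7% | 16.2–31.4% | 12.0–22.1% | 9.8–17.7% |

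The 38% extreme needs zero correlation, the either-site count and log SD 1.2.

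**Step 5: does the stopping rule protect the between-arm tests?** Suppose RAD001 doubles every marker equally in both arms, so there is no true difference between arms. In scenarios where Arm B opens at least 90% of the time, the chance that any of the four between-arm tests is significant is 7–19% (6–19% over all scenarios).

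**Step 6: effect of naming one lead marker.** With two comparisons (Arm A paired; change between arms), the global-null error is 4.8–7.7% unadjusted and 2.4–4.0% with Holm. With equal doubling in both arms, the between-arm error under Holm is 2–5.5%. The small excess over 5% arises because Y is set from Arm A data.

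**The case against.** **It is a pilot.** Section 9.6 says "Given that this is a pilot study", and a pilot with mechanistic endpoints may leave its tests unadjusted. That stands as a reason not to adjust. It does not support a stated overall 0.05, and taking the argument seriously means rewording section 9.5.

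**Phospho-AKT is the implied lead.** Section 9.6 sizes Arm B on it alone, and on that reading the error is only 4.8–7.7%. But section 9.6 presents it as a metric for sizing, names no site, and section 9.3 lists all four signals on an equal footing. The illustration announced by "Below is an illustration of projected data and relevant comparisons" is not visible in the text available and may show which signal is plotted, so the absence of a lead marker is less certain than the absence of an adjustment rule.

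**The arms are sequential.** Section 5.2 opens Arm B only after the Arm A analyses are successfully completed, which could be read as a testing order. It governs enrolment, though, and in section 9.6 the gate is a responder count, not a significance test. It does not act on the four Arm A tests, and it leaves the markers unordered.

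**Success may mean a concordant pattern.** Section 5.5.1 describes the expected result as several changes together. If concordance were required, the any-of-four error would not be the right measure. No such rule is stated, so the objection shows that the success criterion is undefined; it does not show that error is controlled.

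**The upper figures rest on assumptions.** True. With one site counted and log SD 0.3–0.5, all 12 tests give about 10–22%. The lower end is still about twice the stated rate.

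**Conclusion.** The concern holds. Section 9.5 claims an overall 0.05 that sections 9.1 and 9.3 do not deliver. If each test is run at 0.05 and any significant marker may be claimed, the four Arm A tests alone carry about 10–19% under the global null, and they are run whether or not Arm B opens. All 12 carry about 10–38%. The exact size depends on marker correlation, log-scale SD and the phospho-AKT count, none of which the plan states, so only the range should be quoted. The four Arm A tests exceed 5% in every scenario examined. This is a mismatch between a stated property and the analysis. It should be fixed, but it does not invalidate the trial, and naming a lead marker removes most of it.

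**What to change.** Choose one of two options; either is acceptable.

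**Option 1: make the overall 0.05 true.** Name one phospho-AKT measure in advance as lead, and use the same measure for the 50% rule in section 9.6. Make the other markers and the Arm B paired tests supportive. Control 0.05 over two comparisons, Arm A RAD001 versus DMSO and the change in Arm A versus Arm B, for example with Holm, counting the between-arm test as not rejected if X ≤ 3. State that between-arm control is approximate because Y depends on Arm A. Also state that the second comparison is taken to address primary objective 2, since section 2.1 does not mention RAD001 there and the link comes from sections 1.6 and 9.3. A fixed sequence (Arm A, then between arms) is an alternative to Holm with similar error, about 5% under the global null. Its price is no between-arm claim if Arm A fails.

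Cost: edits to 9.1, 9.3, 9.5 and 9.6, and some power. At the first Holm step (0.025, z = 2.241), the sizing formula gives (0.55 − 2.241 × 0.2009)/0.1735 = 0.575, or 71.7% instead of 81.6%, for X = 7, Y = 14. It gives (0.45 − 2.241 × 0.1607)/0.1681 = 0.535, or 70.4% instead of 78.9%, for X = 6, Y = 30. These are worst cases on the sizing metric: once one test rejects, the other returns to 0.05. State the loss; do not enrol more patients to recover it.

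**Option 2: state what the pilot does.** Reword section 9.5 as 0.05 per test, drop the word overall, and report all marker results as unadjusted. Cost: one sentence and a less favourable claim. The phospho-AKT site used for X in section 9.6 should still be named.

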### 5.2 Treatment Period

Patients will receive either A) no presurgical drug treatment, or B) presurgical treatment with Letrozole for 10-21 days prior to surgery. Arm A will enroll patients first until accrual is full (n=10). Following successful completion of molecular analyses to support the first primary objective (To determine whether mTORC1 inhibition with RAD001 increases IRS-1/PI3K/AKT pathway activation in ER+/HER2- breast tumors *ex vivo*), we will proceed to enroll patients in Arm B (presurgical Letrozole, as below in Section 5.2.2). An estimated 10 subjects will be enrolled into Arm B to obtain the necessary evaluable number of subjects (n=10).

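### Section 9.6 claims 80% power at every X that opens Arm B, but at its 15% planning rate Y=30 gives only about 39% at X=4 and 61% at X=5

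*Combined protocol and SAP*

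**What the plan says.** Section 9.6 of the combined protocol and SAP calls a tumor activated if its phospho-AKT signal rises by 50% or more over the DMSO control, and adds that "this scoring system provides a binary metric for sample size determination for Arm B". Arm A is fixed: "tumors from 10 untreated patients in Arm A will be used to determine the frequency with which RAD001 induces AKT activation". For Arm B, the plan expects that at most 15% "of Letrozole-treated tumors will exhibit RAD001-induced AKT activation".

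Given X activated tumors out of 10 in Arm A, Y patients are enrolled in Arm B to detect an effect of Letrozole at p≤0.05 "on RAD001-induced changes in phospho-AKT levels with 80% power (calculated using uncorrected chi-squared statistic"). The table gives Y=30 for X of 4 to 6, Y=14 for 7 to 8 and Y=10 for 9 to 10. The study ends if X is 0 to 3. Nothing restricts the 80% to particular values of X.

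Section 9.5 adds: "All statistical tests will be 2-sided, and the overall type I error will be 0.05". The planned comparison between arms is in Section 9.3: "An additional test will compare the magnitude of change in signal values in Arm A vs. Arm B (2-sided independent t-test"). No power is stated for that test.

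**The concern.** One Y serves three Arm A rates, 40%, 50% and 60%, and the contrast with 15% is much smaller at 40% than at 60%. A Y that meets 80% across the row has to meet it at X=4. If it was set at X=6, the stated power is too high at X=4 and X=5. In that case a decision to enrol 30 patients in Arm B after seeing 4 or 5 activated tumors would rest on a power that the design does not have.

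**Working it through.** **Inputs.** Arm A n=10, p1=X/10, p2=0.15, Y from the table, and the uncorrected chi-squared test (all Section 9.6); two-sided 0.05 (Section 9.5). Section 5.4 replaces non-evaluable subjects, so 10 and Y are taken as evaluable numbers.

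**Formula** (normal approximation to the uncorrected chi-squared test):

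- p̄ = (10·p1 + Y·p2)/(10 + Y)
- s0 = √[p̄(1−p̄)(1/10 + 1/Y)]
- s1 = √[p1(1−p1)/10 + p2(1−p2)/Y]
- power = Φ[(p1 − p2 − 1.96·s0)/s1]

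**The plan's own 80%, where it can be reproduced**

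- X=6, Y=30: p̄ = (6+4.5)/40 = 0.2625, s0 = 0.1607, s1 = 0.1681. Φ[(0.45 − 0.315)/0.1681] = Φ(0.80) = 78.9%.
- X=7, Y=14: p̄ = (7+2.1)/24 = 0.3792, s0 = 0.2009, s1 = 0.1735. Φ[(0.55 − 0.394)/0.1735] = Φ(0.90) = 81.6%.

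Both land on about 80%, which indicates that this is the plan's method and that 15% is its planning rate.

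**The two values in question**

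- X=4, Y=30: p̄ = (4+4.5)/40 = 0.2125, s0 = 0.1494, s1 = 0.1681. Φ[(0.25 − 0.293)/0.1681] = Φ(−0.25) = 40.0%.
- X=5, Y=30: p̄ = (5+4.5)/40 = 0.2375, s0 = 0.1554, s1 = 0.1710. Φ[(0.35 − 0.305)/0.1710] = Φ(0.27) = 60.5%.

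**All continuing values at p2=0.15.** The exact column sums the probabilities of all pairs of binomial counts for which the uncorrected chi-squared test rejects. The conditional column holds X at its observed value and lets only the Arm B count vary, with rejection in favour of a lower Arm B rate.

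| X | Y | Formula | Exact | Conditional on X |
|---|---|---|---|---|
| 4 | 30 | 40.0% | 39.3% | 32% |
| 5 | 30 | 60.5% | 60.9% | 71% |
| 6 | 30 | 78.9% | 79.6% | 93% |
| 7 | 14 | 81.6% | 80.5% | 95% |
| 8 | 14 | 94.2% | 93.3% | 99% |
| 9 | 10 | 98.3% | 97.0% | 99% |
| 10 | 10 | >99.9% | >99.9% | >99.9% |

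On the unconditional definition, Y=14 meets 80% at the least favourable X in its row, while Y=30 does so (within rounding) only at the most favourable X in its row.

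**In counts.** At 15%, 0.15 × 30 = 4.5 activated tumors are expected in Arm B.

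- Against 4/10 in Arm A, the test gives p=0.031 for 3/30, p=0.068 for 4/30 and p=0.126 for 5/30. It therefore needs 3 or fewer, and a result near the planning rate is not significant.
- Against 5/10, it gives p=0.035 for 5/30 and p=0.066 for 6/30. It needs 5 or fewer.

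**Lower Letrozole rates, Y=30**

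| Arm B rate | X=4 exact / conditional | X=5 exact / conditional |
|---|---|---|
| 15% | 39% / 32% | 61% / 71% |
| 10% | 56% / 65% | 76% / 93% |
| 5% | 75% / 94% | 89% / 99.7% |

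**Would a larger Y help?** Not at 15% with Arm A fixed at 10. As Y grows without limit, s0 tends to √(0.1275/10) = 0.1129. The formula then tends to Φ[(0.25 − 0.221)/0.1549] = 57% at X=4 and Φ[(0.35 − 0.221)/0.1581] = 79% at X=5.

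**The case against.** **15% is an upper limit, not a point estimate.** Power does rise if the true rate is lower. But a Y meant to cover any rate up to 15% has to work at 15%, and 15% is the rate that reproduces the plan's figure at X=6 and X=7. By the formula, reaching 80% with Y=30 needs an Arm B rate of about 3% at X=4 or 8% at X=5, and the plan states neither.

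**Y is chosen after X is known, so conditional power is the natural measure.** This is a fair reading, and part of it stands: the size of the shortfall at X=5 depends on the definition. Conditionally, X=5 is at 71% for a 15% rate and passes 80% once the rate falls to 13% (81%). X=6 is then comfortably powered. X=4 remains at 32% for a 15% rate and needs a rate of about 7% or less.

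**Perhaps 30 per arm was assumed.** That would give 84% at X=5 but still only 59% at X=4, and Section 9.6 fixes Arm A at 10.

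**This is a pilot, and the binary metric is not analysed.** Both are true, and they limit the consequence. They do not make the printed power correct, and Section 9.6 gives no other statistical basis for Y=30.

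**Conclusion.** The point holds: the blanket 80% is wrong as written. It fails at X=4 on either definition of power, by a wide margin. It also fails at X=5 on either definition at a 15% rate, though by an amount that depends on the definition. The other five values of X that open Arm B are at or above 80% within rounding.

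The figures assume a true Arm A rate of X/10 (for the unconditional results), a 15% Letrozole rate and evaluable numbers of 10 and Y. They concern the binary sizing comparison only and say nothing about the power of the t-test in Section 9.3. The error is in the design figure behind Y=30, not in a planned analysis. It should be fixed.

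**What to change.** In Section 9.6, replace the single 80% with power by X, using one method throughout. Suggested text, on exact values:

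> Power of the binary sizing comparison (phospho-AKT increase of at least 50%; uncorrected chi-squared, two-sided 0.05; Arm A n=10 with true rate X/10; Letrozole rate 15%; exact calculation) is about 39% at X=4, 61% at X=5, 80% at X=6, 81% at X=7, 93% at X=8, 97% at X=9 and over 99.9% at X=10. Y=30 does not give 80% power at X=4 or X=5 at this rate. These figures do not apply to the t-test in Section 9.3.

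This discloses the shortfall and does not remove it; as shown above, enlarging Arm B alone could not remove it at a 15% rate. The cost is a few lines of wording and a less favourable stated power at two values of X. No patients are added.

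A separate, minor point: Section 5.2 says "An estimated 10 subjects will be enrolled into Arm B to obtain the necessary evaluable number of subjects (n=10"), while the Section 9.6 table allows 10, 14 or 30. The two should be reconciled, for example by a cross-reference from Section 5.2 to the table.
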